10.6.3 Analysis of Safety

The primary analysis will be based on the Total vaccinated cohort. If the percentage of enrolled subjects excluded from the ATP cohort for safety is more than 5%, a second analysis based on this ATP cohort will be performed to complement the Total vaccinated cohort analysis.

The percentage of subjects with at least one local adverse event (solicited and unsolicited), with at least one general adverse event (solicited and unsolicited) and with any adverse event during the 4-day solicited follow-up period will be tabulated with exact

95% CI after each vaccine dose and overall. The percentage of doses followed by at least one local adverse event (solicited and unsolicited), by at least one general adverse event (solicited and unsolicited) and by any adverse event will be tabulated, overall vaccination course, with exact 95% CI.

The percentage of subjects reporting each individual solicited local and general adverse event during the 4-day solicited follow-up period will be tabulated with exact 95% CI. The percentage of doses followed by each individual solicited local and general adverse event will be tabulated, overall vaccination course, with exact 95% CI.

The same tabulation will be performed for grade 3 adverse events and for adverse events with relationship to vaccination.

The proportion of subjects with at least one report of unsolicited adverse event classified by the Medical Dictionary for Regulatory Activities (MedDRA), and reported up to 30 days after vaccination will be tabulated with exact 95% CI. The same tabulation will be performed for grade 3 unsolicited adverse events and for unsolicited adverse events with a relationship to vaccination.

Serious adverse events and withdrawal due to adverse event(s) will be described in detail.

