- At 12 months of age, to assess the reactogenicity and safety of the 10 µg meningococcal A and C polysaccharides when given to subjects primed with either Tritanrix™-HepB/Hib-MenAC or with Tritanrix™-HepB/ Hiberix™.

Study design

- Experimental design: 2 parallel groups of 140 subjects each to receive either of the following vaccines:
 - Tritanrix™-HepB/Hib-MenAC
 - Tritanrix™-HepB/Hiberix™
- Active control group (Tritanrix™-HepB/Hiberix™)
- Indication: primary vaccination of infants according to the Expanded Program of Immunization (EPI) schedule (6, 10, 14 weeks of age).
- BCG and OPV vaccines can be given at birth or up to at least 2 weeks before study start. OPV can then be given concomitantly with the study vaccines at 6, 10 and 14 weeks of age or at any time during the study, whichever is more appropriate. At 9 months of age, all subjects will receive measles and yellow fever vaccines.
- At 12 months of age, all subjects will be evaluated for antibody persistence and will be administered 10 µg of each plain meningococcal serogroup A and C polysaccharides (one fifth of a dose of Mencevax™ AC) to evaluate the immune memory induced by vaccination.
- After study end, one dose of Mencevax™ ACWY will be offered to the Tritanrix™-HepB/Hiberix™ control group to protect them against meningococcal diseases of these serogroups: Mencevax™ ACWY will be given when the child is two years of age, or, if a meningitis epidemic occurs, earlier in the second year of life.

- Treatment allocation: randomized (1:1)
- Blinding: Double-blind
- Study duration per subject: approximately **22.5 months to include the retrospective follow-up of SAE(s) up to the time that subjects are at least 24 months of age.**
- Data collection: Hard copy Case Report Form (CRF)
- For all subjects: 4 blood samples (3.5 ml):
 - immediately before the first dose of the primary vaccination course
 - one month after the third dose of the primary vaccination course
 - just prior to administration of the plain polysaccharides of serogroups A and C
 - one month after the administration of the plain polysaccharides of serogroups A and C.
- 4-day follow-up of solicited local and general symptoms after each dose.
- One month follow-up for unsolicited symptoms after each dose.
- Reporting of serious adverse events during the entire study period.

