Appendix G: Vaccine supplies, packaging and accountability

It is NOT permitted to use any of the supplies provided by GSK Biologicals for purposes other than those specified in the protocol. Unused supplies will be collected by GSK Biologicals on completion of the study. Used vaccine vials can be disposed on site according to local biosafety standard for disposal of biological waste material.

1. Vaccine supplies

GSK Biologicals will supply the following amounts of numbered doses of study vaccines, sufficient to administer 3 doses to all subjects as described in the present protocol.

- 420 doses of Hib-MenAC vaccine in monodose vials
- 420 doses of Hiberix™ vaccine in monodose vials
- 1260 doses of Tritanrix™-HepB vaccine in monodose vials
- 280 doses of Mencevax™ AC
- 560 doses of 0.5 ml diluent for the Mencevax™ AC vaccine

An additional quantity of at least 5% of Tritanrix™-HepB and Hiberix™ will be supplied for replacement in case of breakage, bad storage conditions or any other reason that would make the vaccine unusable (i.e., given by mistake to another subject).

All monodose vials must be accounted for on the form provided.

In case of suboptimal response to an antigen (refer to Section 5.5.4) GSK Biologicals will also supply doses of Mencevax™ ACWY or Tritanrix™-HepB/Hiberix™ vaccines on a case by case basis.

2. Vaccine packaging

The vaccines will be packed in labelled boxes. In order to ensure the double blind of the study, all vaccine boxes will be identical (size and appearance), despite the different number of vials needed for reconstitution of the vaccines. Only the vaccination team will open the boxes for reconstitution and administration of the vaccine so only the vaccination team will know which vaccine is contained in the individual boxes (see section 6.4). The box label will contain, as a minimum, the following information: study number, subject number, lot number (or numbers, when double-blind), instructions for vaccine administration.

3. Vaccine accountability

The investigator or pharmacist must sign a statement that he/she has received the clinical supplies for the study. At all times the figures on supplied, used and remaining vaccine

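### Exact 95% CIs on pooled per-dose reactogenicity percentages treat up to three doses per infant as independent and are likely somewhat too narrow; the consequence is minor

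*Protocol*

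**What the plan says.** Section 10.6.3 of the protocol plans two kinds of reactogenicity table for the primary course.

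- **Per subject.** Percentages of infants with at least one local, general or any event are given after each dose and overall, with exact 95% CIs. For individual symptoms the section plans "The percentage of subjects reporting each individual solicited local and general adverse event during the 4-day solicited follow-up period", also with exact CIs.
- **Per dose, pooled over the course.** For individual solicited symptoms: "The percentage of doses followed by each individual solicited local and general adverse event will be tabulated, overall vaccination course, with exact 95% CI". The percentages of doses followed by a local event, by a general event and "by any adverse event will be tabulated, overall vaccination course, with exact 95% CI" are treated the same way.

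The section then extends the tables: "The same tabulation will be performed for grade 3 adverse events and for adverse events with relationship to vaccination".

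The design has "2 parallel groups of 140 subjects each to receive either of the following vaccines". Appendix G plans supplies "sufficient to administer 3 doses to all subjects as described in the present protocol", including "420 doses of Hib-MenAC vaccine in monodose vials". The protocol nowhere names the infant as a cluster or a correlation-adjusted interval for these percentages. The booster safety analysis in Section 10.7.2 has no per-dose percentages.

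**The concern.** An exact CI for a percentage is the Clopper-Pearson binomial interval, and its coverage guarantee requires independent trials. Up to three of the pooled doses come from the same infant, given the same vaccine. In Section 8.6.1, pain, irritability, drowsiness and loss of appetite are graded on the child's behaviour, so a child who reacts visibly once may well do so again. The rule in Section 10.5 that missing symptom reports count as no symptoms can add to the correlation, because a child with repeated missing reports contributes repeated zeros.

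Positive correlation means 420 doses carry less information than 420 independent observations. The interval labelled 95% would then cover less often than stated, and its upper limit, the side of most interest for safety, would be too low. The protocol itself fixes both the unit and the interval, so this is not a detail left open for the SAP.

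**Working it through.** **Inputs from the protocol.** 140 infants per group (synopsis and Section 3); 3 doses per infant (Appendix G). Pooled denominator if all infants complete: 140 × 3 = 420, which agrees with the 420 Hib-MenAC doses in Appendix G. The protocol states no expected interval width for these tables, so there is no figure of its own to reproduce.

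**Assumptions, not in the protocol.** ICC ρ between doses in the same infant, from 0 to 0.5; event rate p from 5% to 50% of doses, equal at all three doses.

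**Formulas.**
- Design effect with m = 3 doses per infant: 1 + (m − 1)ρ = 1 + 2ρ.
- Factor by which the standard error is understated: √(1 + 2ρ).
- Effective number of doses: 420 / (1 + 2ρ).
- Coverage of the planned interval: the number of doses with a reaction is the sum of 140 independent beta-binomial counts of size 3, with parameters p(1 − ρ)/ρ and (1 − p)(1 − ρ)/ρ. Its exact distribution was obtained by convolution, and the probabilities of all counts whose Clopper-Pearson interval at n = 420 contains p were added.
- Adjusted interval: Clopper-Pearson form at the effective number of doses.

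| ρ | Design effect | Effective doses | SE factor | Coverage of planned CI, p = 5-50% | CI at p = 30% | CI at p = 5% |
|---|---|---|---|---|---|---|
| 0 | 1.0 | 420 | 1.00 | 95-96% | 25.7-34.6% (as planned) | 3.1-7.5% (as planned) |
| 0.05 | 1.1 | 382 | 1.05 | 94-95% | 25.4-34.9% | 3.0-7.7% |
| 0.1 | 1.2 | 350 | 1.10 | 93-94% | 25.2-35.1% | 3.0-7.8% |
| 0.3 | 1.6 | 262.5 | 1.26 | 89% | 24.5-35.9% | 2.7-8.4% |
| 0.5 | 2.0 | 210 | 1.41 | 84-85% | 23.9-36.7% | 2.5-8.9% |

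Under independence the planned interval is valid and slightly conservative. At ρ = 0.05 that conservatism nearly hides the problem.

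**Rates that differ by dose.** With rates p₁, p₂, p₃ and vⱼ = pⱼ(1 − pⱼ), the variance of an infant's count is Σvⱼ + 2ρ Σ√(vⱼvₖ) over the three pairs. The planned interval uses 3p(1 − p) at the mean rate, here 3 × 0.3 × 0.7 = 0.63.
- Rates 40/30/20%, ρ = 0.1: Σvⱼ = 0.24 + 0.21 + 0.16 = 0.61 and the pair sum is 0.604. The variance is 0.61 + 0.2 × 0.604 = 0.731, so the SE factor is √(0.731/0.63) = 1.08 instead of 1.10.
- Rates 50/30/10%: Σvⱼ = 0.25 + 0.21 + 0.09 = 0.55 and the pair sum is 0.517. At ρ = 0.1 the factor is √(0.653/0.63) = 1.02. At ρ = 0.3 it is √(0.860/0.63) = 1.17 instead of 1.26.

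Unequal rates therefore reduce the effect but do not remove it in these examples.

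**The case against.** The strongest reply is that nothing of consequence rests on these intervals. Section 10.6.3 plans no reactogenicity test, margin, group difference or decision rule; the only inferential sequence is the seven immunogenicity steps in Section 10.6.2. Safety oversight in Sections 5.1.3 and 8.7 works from SAE reports, grade 3 listings and blinded reactogenicity review, not from per-dose CIs. The secondary objective concerns reactogenicity after each dose and overall, and the per-subject tables serve it with valid intervals. All of this stands, and it limits the point to a minor one.

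The size is also uncertain. The protocol gives no ICC, and equal rates across doses put the figures toward the upper end for a given ICC. That stands too. The direction rests on positive correlation being likely; the amount cannot be known from the document.

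Two stronger readings are tempting. A reader might infer that the planned analysis will overstate the certainty of a difference between groups. No such comparison is planned, so the effect is confined to someone comparing two descriptive intervals by eye. A reader might also infer that the intervals certainly fail to cover at 95%. That depends on the ICC: at 0.05 coverage is still about 94-95%.

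Finally, GEE with robust variance, or a bootstrap over infants, is not a safe general remedy. With no events in the grade 3 or vaccine-related tables, the bootstrap interval collapses to 0-0%, and robust variance is undefined or unstable when events are few. This objection stands and shapes the fix.

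**Conclusion.** The point holds as a minor error in a stated method. The pooled per-dose intervals rest on an independence assumption that repeated dosing of the same infant makes doubtful, and under the likely positive correlation they are too narrow. For an assumed ICC between 0.05 and 0.5, 420 doses per group and equal rates at each dose, the understatement of the standard error runs from about 5% to 41% of its planned value, with coverage falling from just under nominal to about 84-85%. At ICC 0.3 the upper limit moves from 34.6% to 35.9% at a 30% rate, and from 7.5% to 8.4% at a 5% rate.

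The co-primary conclusions, the per-subject tables, the single-dose tables and the booster phase are unaffected.

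**What to change.** Amend Section 10.6.3, or state in the SAP, that percentages of doses pooled over the primary course are given either without a CI or with an interval that takes the infant as the cluster. A suitable choice for the second option is an exact-type interval at the effective sample size, with the ICC estimated from the data; it is more stable than GEE or a bootstrap when events are few. Where a table has zero or very few events, as may happen for grade 3 events, give no cluster-based CI and refer to the per-subject table. Keep the exact CIs for per-subject percentages and for each single dose, where each infant contributes one observation.

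The cost is a sentence of text and a little programming. No new data are needed. The downside is a somewhat wider interval, or none, in the per-dose tables.

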10.7 Final Analyses for the booster vaccination

10.7.1 Analysis of immunogenicity

The analysis of antibody persistence and the analysis of immune memory will be respectively based on the ATP cohort for safety and the ATP cohort for immune memory. If, for any vaccine group, the percentage of enrolled subjects with serological results excluded from an ATP cohort is more than 5%, a second analysis based on the Total vaccinated cohort will be performed to complement the ATP analysis.

The analysis of immunogenicity will be as follows:

Analysis of antibody persistence

For each treatment group, one month after the third dose of the primary vaccination course and just before the administration of one fifth of a dose of Mencevax™ AC:

- Geometric Mean antibody Concentrations/Titers (GMCs/GMTs) with 95% confidence intervals (CIs) will be tabulated for each antibody. Calculation of the

GMCs/GMTs is performed by taking the anti-log of the mean of the log concentration/titer transformations.

- Seropositivity / seroprotection rates with exact 95% CIs will be calculated.
- Antibody concentrations/titers pre-booster will also be investigated using reverse cumulative curves for each antigen and serotype.

Analysis of immune memory

For each treatment group, just before and one month after the administration of one fifth of a dose of MencevaxTM AC:

- Geometric Mean antibody Concentrations/Titers (GMCs/GMTs) with 95% confidence intervals (CIs) will be tabulated for each antibody. Calculation of the GMCs/GMTs is performed by taking the anti-log of the mean of the log concentration/titer transformations.
- Seropositivity / seroprotection rates with exact 95% CIs will be calculated.
- Antibody concentrations/titers post-booster will also be investigated using reverse cumulative curves for each antigen and serotype.

The ratio of the GMCs/GMTs between the TritanrixTM-HepB/Hib-MenAC group and the TritanrixTM-HepB/HiberixTM group one month after the administration of one fifth of a dose of MencevaxTM AC, will be computed with its 95% CI. The ratio and its 95% CI will be computed using an ANOVA model on the log-transformed concentration/titer with group effect as regressor.

10.7.2 Analysis of safety

All analyses will be based on the Total vaccinated cohort. If the percentage of enrolled subjects excluded from the ATP cohort for safety is more than 5%, a second analysis based on this ATP cohort will be performed to complement the Total vaccinated cohort analysis.

The percentage of subjects with at least one local adverse event (solicited and unsolicited), with at least one general adverse event (solicited and unsolicited) and with any adverse event during the 4-day solicited follow-up period will be tabulated with exact 95% CI after each vaccine dose and overall.

The percentage of subjects reporting each individual solicited local and general adverse event during the 4-day solicited follow-up period will be tabulated with exact 95% CI.

The same tabulation will be performed for grade 3 adverse events and for adverse events with relationship to vaccination.

The proportion of subjects with at least one report of unsolicited adverse event classified by the Medical Dictionary for Regulatory Activities (MedDRA), and reported up to 30 days after vaccination will be tabulated with exact 95% CI. The same tabulation will be performed for grade 3 unsolicited adverse events and for unsolicited adverse events with a relationship to vaccination.

Serious adverse events and withdrawal due to adverse event(s) will be described in detail.

10.8 Reporting of final analyses

A final analysis for the primary vaccination course will be carried out as soon as all data up to Visit 4 have been collected in order to analyse the immunogenicity endpoints (including the co-primary endpoints) and the analysis of safety/reactogenicity for the primary vaccination course (refer to Section 10.6 for details about this analysis). A report based on this analysis will be written and will be made available to the Principal Investigator and the sponsors involved in this study. The access to the individual treatment code will be limited to the statistician in charge of this analysis.

A final analysis for the booster vaccination will be carried out based on all data collected up to one month after the administration of one fifth of a dose of Mencevax™ AC. An annex report based on the final analysis for the booster vaccination will be provided.

Serious adverse events reported during the extended follow-up period (i.e. from visit 7 up to 24 months of age) will be reported in a separate annex report.

(Amendment 7: 12 April 2006)

Appendix A: World Medical Association Declaration of Helsinki

Recommendations guiding physicians
in biomedical research involving human subjects

Adopted by the 18th World Medical Assembly
Helsinki, Finland, June 1964

and amended by the
29th World Medical Assembly
Tokyo, Japan, October 1975
35th World Medical Assembly
Venice, Italy, October 1983
41st World Medical Assembly
Hong Kong, September 1989
and the
48th General Assembly
Somerset West, Republic of South Africa, October 1996

INTRODUCTION

It is the mission of the physician to safeguard the health of the people. His or her knowledge and conscience are dedicated to the fulfilment of this mission.

The Declaration of Geneva of the World Medical Association binds the physician with the words, "The health of my patient will be my first consideration," and the International Code of Medical Ethics declares that, "A physician shall act only in the patient's interest when providing medical care which might have the effect of weakening the physical and mental condition of the patient."

The purpose of biomedical research involving human subjects must be to improve diagnostic, therapeutic and prophylactic procedures and the understanding of the etiology and pathogenesis of disease.

In current medical practice most diagnostic, therapeutic or prophylactic procedures involve hazards. This applies especially to biomedical research.

Medical progress is based on research which ultimately must rest in part on experimentation involving human subjects.

In the field of biomedical research a fundamental distinction must be recognized between medical research in which the aim is essentially diagnostic or therapeutic for a patient, and medical research, the essential object of which is purely scientific and without implying direct diagnostic or therapeutic value to the person subjected to the research.

Special caution must be exercised in the conduct of research which may affect the environment, and the welfare of animals used for research must be respected.

Because it is essential that the results of laboratory experiments be applied to human beings to further scientific knowledge and to help suffering humanity, the World Medical Association has prepared the following recommendations as a guide to every physician in biomedical research involving human subjects. They should be kept under review in the future. It must be stressed that the standards as drafted are only a guide to physicians all over the world. Physicians are not relieved from criminal, civil and ethical responsibilities under the laws of their own countries.

I. BASIC PRINCIPLES

1. Biomedical research involving human subjects must conform to generally accepted scientific principles and should be based on adequately performed laboratory and animal experimentation and on a thorough knowledge of the scientific literature.
2. The design and performance of each experimental procedure involving human subjects should be clearly formulated in an experimental protocol which should be transmitted for consideration, comment and guidance to a specially appointed committee independent of the investigator and the sponsor provided that this independent committee is in conformity with the laws and regulations of the country in which the research experiment is performed.
3. Biomedical research involving human subjects should be conducted only by scientifically qualified persons and under the supervision of a clinically competent medical person. The responsibility for the human subject must always rest with a medically qualified person and never rest on the subject of research, even though the subject has given his or her consent.
4. Biomedical research involving human subjects cannot legitimately be carried out unless the importance of the objective is in proportion to the inherent risk to the subject.
5. Every biomedical research project involving human subjects should be preceded by careful assessment of predictable risks in comparison with foreseeable benefits to the

subject or to others. Concern for the interests of the subject must always prevail over the interests of science and society.

6. The right of the research subject to safeguard his or her integrity must always be respected. Every precaution should be taken to respect the privacy of the subject and to minimize the impact of the study on the subject's physical and mental integrity and on the personality of the subject.
7. Physicians should abstain from engaging in research projects involving human subjects unless they are satisfied that the hazards involved are believed to be predictable. Physicians should cease any investigation if the hazards are found to outweigh the potential benefits.
8. In publication of the results of his or her research, the physician is obliged to preserve the accuracy of the results. Reports of experimentation not in accordance with the principles laid down in this Declaration should not be accepted for publication.
9. In any research on human beings, each potential subject must be adequately informed of the aims, methods, anticipated benefits and potential hazards of the study and the discomfort it may entail. He or she should be informed that he or she is at liberty to abstain from participation in the study and that he or she is free to withdraw his or her consent to participation at any time. The physician should then obtain the subject's freely-given informed consent, preferably in writing.
10. When obtaining informed consent for the research project the physician should be particularly cautious if the subject is in a dependent relationship to him or her or may consent under duress. In that case the informed consent should be obtained by a physician who is not engaged in the investigation and who is completely independent of this official relationship.
11. In case of legal incompetence, informed consent should be obtained from the legal guardian in accordance with national legislation. Where physical or mental incapacity makes it impossible to obtain informed consent, or when the subject is a minor, permission from the responsible relative replaces that of the subject in accordance with national legislation.

Whenever the minor child is in fact able to give a consent, the minor's consent must be obtained in addition to the consent of the minor's legal guardian.

12. The research protocol should always contain a statement of the ethical considerations involved and should indicate that the principles enunciated in the present Declaration are complied with.

II. MEDICAL RESEARCH COMBINED WITH PROFESSIONAL CARE (Clinical research)

1. In the treatment of the sick person, the physician must be free to use a new diagnostic and therapeutic measure, if in his or her judgement it offers hope of saving life, re-establishing health or alleviating suffering.
2. The potential benefits, hazards and discomfort of a new method should be weighed against the advantages of the best current diagnostic and therapeutic methods.
3. In any medical study, every patient - including those of a control group, if any - should be assured of the best proven diagnostic and therapeutic method. This does not exclude the use of inert placebo in studies where no proven diagnostic or therapeutic method exists.
4. The refusal of the patient to participate in a study must never interfere with the physician-patient relationship.
5. If the physician considers it essential not to obtain informed consent, the specific reasons for this proposal should be stated in the experimental protocol for transmission to the independent committee (I, 2).
6. The Physician can combine medical research with professional care, the objective being the acquisition of new medical knowledge, only to the extent that medical research is justified by its potential diagnostic or therapeutic value for the patient.

III. NON-THERAPEUTIC BIOMEDICAL RESEARCH INVOLVING HUMAN SUBJECTS (Non-clinical biomedical research)

1. In the purely scientific application of medical research carried out on a human being, it is the duty of the physician to remain the protector of the life and health of that person on whom biomedical research is being carried out.
2. The subjects should be volunteers - either healthy persons or patients for whom the experimental design is not related to the patient's illness.
3. The investigator or the investigating team should discontinue the research if in his/her or their judgement it may, if continued, be harmful to the individual.
4. In research on man, the interest of science and society should never take precedence over considerations related to the well being of the subject.

